**Inclusion / Exclusion Criteria:** Based on previous studies, we will **include participants who:**

- 1) Self-report having had lower back pain on most days for greater than three months.
- 3) Can complete a 10 second semi-tandem stand and walk 8' in 6.0 seconds.
- 4) Report they are not satisfied with their current state of functional ability, based on reporting "dissatisfied" with at least one aspect of physical function on the Satisfaction with Physical Function Scale.
- 5) Can safely participate in the intervention based upon the physical therapist baseline examination and clinical expertise.

Veterans will be **excluded if they have:**

- 1) acute unilateral or bilateral sciatica (based on Physical Therapist exam at baseline); isolated coccyx pain (based on self-report at screener);
- 2) dementia or other significant cognitive impairment;
- 3) movement or motor neuron disorders (e.g., Parkinson's Disease, Multiple Sclerosis, Amyotrophic Lateral Sclerosis);
- 4) rheumatoid arthritis, fibromyalgia, or other systemic rheumatic disease;

- 5) hospitalization for a stroke, myocardial infarction, heart failure, or coronary artery revascularization in the past 3 months;
- 6) significant hearing impairment (must be able to talk on the telephone);
- 7) psychosis or current, uncontrolled substance abuse disorder;
- 8) legally blind;
- 9) any other health conditions determined by the study team to be contraindications to performing mild to moderate home exercises.

Based on our prior and ongoing studies at the Durham VAMC that have similar recruitment and procedural methods, we are confident we can enroll n=60 older veterans with cLBP within the proposed recruitment period for this study. Study participants excluded after consent due to the presence of sciatica or other functional limitations or health problems as determined by the physical therapist at baseline will not be randomized and thus not included in our total enrollment goal, i.e. we plan to consent enough participants such that a total of n=60 are eligible to participate, having met the eligibility criteria assessed following consent.

**Physical Activity Program:** The PA program for this study is based on three general principles: 1.) Feasibility to disseminate widely within the VA healthcare system. 2.) Recommendations for PA among older adults (e.g. mild to moderate intensity). 3.) Recommendations for PA programs for individuals with cLBP. This PA program will include 12 weeks of home-based exercise, including stretching, strengthening, and aerobic activities, and will follow Department of Health and Human Services recommendations for PA for older adults. At the baseline visit, the physical therapist will provide participants with basic information on appropriate PA techniques and an individualized PA program, guided by baseline assessments. PA programs will be based on a core set of strengthening and stretching exercises (in addition to regular aerobic activity), which cover major muscle groups and functional tasks. The physical therapist will provide personalized recommendations from within this set, including specification of the specific exercises assigned (e.g., starting with a smaller number of exercises at the beginning of the program, easier options for those with more limited function) and duration / number of repetitions for each exercise; the therapist may also add other exercises to address specific deficits and progression. Following this, the physical therapist will conduct approximately 30-minute phone calls at weeks 1, 4, and 9, and an exercise counselor will conduct phone calls at weeks 1-3, 5-8, and 10-12. We have chosen this “joint delivery” model to combine the clinical expertise of the physical therapist (e.g., addressing specific functional and clinical issues and recommending appropriate modifications and progression of activity) and the motivational interviewing expertise of the exercise counselor, to foster adherence. If participants report any pain increases or other clinical issues during a telephone call with the exercise counselor, the physical therapist may follow up with a telephone call to address these problems. The exercise counselor may recommend that participants decrease their overall activity level or discontinue any specific pain-inducing exercises until the physical therapist gives the participant further instructions. We will document these situations, and this will be important information for development of a larger clinical trials (e.g., whether more frequent calls from the physical therapist during a particular phase of the program may be advantageous). Although specific PA recommendations will be given by the physical therapist, the exercise counselor will help participants to identify and problem-solve general barriers to achieving PA goals, such as lack of time, lack of motivation, etc. The exercise counselor will ask participants about their PA during the prior week, and based on this information will help them to refine action plans for achieving PA goals for the upcoming week. All calls will use a semi-structured approach, where the overall content will be standardized across participants, but the physical therapist and exercise counselor will have flexibility to address patient-specific concerns.

We will also provide participants with resources for facilitating PA. First, we will give participants a handout containing instructions for general strengthening and stretching exercises appropriate for older adults with cLBP. These exercises will not focus only on the low back, since recommendations indicate that more general exercise is appropriate for this patient group. However, these exercises will avoid positions and activities that tend to be painful or difficult for individuals with LBP and those with extremely low functional abilities. These booklets will contain both simple written instructions and high quality photographs for each exercise, similar to those [name] and colleagues have developed for other studies. Second, we will provide participants with a copy of an exercise video called *Take Control With Exercise*, created by the Arthritis Foundation. Although

developed for individuals with various types of arthritis, this exercise video is very appropriate for older adults with cLBP and shows patients with various functional abilities completing the exercises.

One challenge in the area of PA is that of adherence. We will employ several strategies for fostering adherence to PA goals. First, we will ask participants to develop and document specific plans for when they will complete their PA. Second, we will help participants to develop PA action plans that are reasonable for them to achieve. Specifically, the exercise counselor will ask participants to rate their self-efficacy for completing action plans with a standardized question (i.e., How confident are you that you can complete these action plans, on a scale of 0-10, with 0 being not at all confident and 10 being very confident?). If participants rate their self-efficacy lower than 7, the exercise counselor will recommend they revise their plans so they are more confident they will be able to carry them out. Prior research has shown that a self-efficacy rating of 7 or above is associated with a greater likelihood of accomplishing a goal or plan, and this strategy has proven successful in our prior and ongoing studies. Third, during each telephone call the exercise counselor will ask about any barriers participants encountered since the last phone call. This will be in the form of an open-ended question “What barriers did you face to completing your physical activity action plans since we spoke last?”. The exercise counselor will then guide participants in a process of problem-solving any barriers noted, which will be incorporated into action plans for the next week.

### CBT-P Intervention

Participants in this group will additionally receive instruction in CBT-P skills, woven into each telephone-based session and with specific application to PA (e.g., overcoming pain-related barriers and managing pain associated with activity). This intervention will be delivered by the exercise counselor, who will be cross-trained to deliver CBT-P, as we have successfully done in prior studies. We will utilize modules we have previously developed for teaching these skills in a behavioral intervention for osteoarthritis. Participants will receive written materials for instruction in each skill, as well as an audio recording to facilitate progressive muscle relaxation. The specific topics included will be: activity pacing, breathing relaxation, distraction, progressive muscle relaxation, and cognitive restructuring. Consistent with a cognitive-behavioral approach, initial strategies will stress behavioral strategies whereas cognitive strategies are introduced later in treatment. The exercise counselor will discuss each skill described below at two telephone calls. The first call will begin with education about the specific strategy, including a rationale for its application to the management of cLBP-related pain. Participants will then briefly rehearse the new skill with the counselor. The counselor will next discuss potential facilitators and barriers to practicing and applying the new skill. Finally, the counselor will help participants to develop a plan for independent practice and application of these strategies to manage symptoms. Participants will be provided with a log to record their practice of these skills. During the second call for each skill, the participant and counselor will work collaboratively to review progress towards mastering, adapting, and applying these new skills to meet the participant’s individual goals.

The following are brief descriptions of each topic addressed in this portion of the intervention:

Activity Pacing: Activity pacing is a simple but essential principle for managing cLBP. Strategies for pacing activities include: going slower through normal daily activities, taking periodic rest periods, and breaking up activities into smaller tasks. When instructed in activity pacing, participants will be asked to identify regular tasks that sometimes result in increased pain. Then participants will be guided in a process of choosing a strategy to pace that activity to reduce the load on the body.

Breathing Relaxation: cLBP can be physically and emotionally taxing, and both physical and emotional tension can increase pain perception. Relaxation exercises are a well-documented method for reducing bodily tension, arousal, and anxiety, and for increasing a sense of control and well-being. Breathing relaxation entails slow, deep, rhythmic breathing, inhaling through the nose and exhaling through the mouth. We will provide participants with audio instructions on CD for relaxation exercises.

Distraction: Distraction involves changing the focus of attention when pain is experienced, or in anticipation of a painful experience. This skill is most useful during short, discrete tasks, such as walking up stairs. Participants will be asked to identify activities that sometimes result in increased pain and to think of something pleasant or engage their mind in another task during this activity.

Progressive Muscle Relaxation: Progressive muscle relaxation involves systematically tensing and relaxing each muscle group and can be effective in producing deep relaxation and reducing muscle tension. We will provide participants with audio instructions on CD for relaxation exercises.

**Cognitive Restructuring (“Positive Self-Talk”):** Cognitive restructuring is a technique for identifying and correcting negative thought patterns, which may be associated with maladaptive behaviors and emotional responses, as well as greater pain. This technique involves identifying “automatic thoughts”, examining and challenging the assumptions behind those thoughts, and replacing them with more rational beliefs. Through repeated practice, participants learn to recognize and modify negative thinking and to create more adaptive and rational perceptions of situations, others, and themselves.

**Measures and Data Collection:** Outcomes will be measured in person at the Durham VAMC at baseline and 12-week follow up. Our primary outcomes consist of general physical function measures, assessed both objectively and via patient self-report:

**Primary Physical Function Outcomes:** *Timed Get Up-and-Go*: This test requires the participants to stand from a standard arm chair, walk 3 meters and then return to sitting in the same chair. The timed get up-and-go test has demonstrated excellent reliability and correlates well with other standard measures such as gait speed, self-report and clinical report indices of function, and is predictive of who can safely ambulate.

***PROMIS Health Assessment Questionnaire (PROMIS-HAQ):*** The PROMIS HAQ is a self-reported physical function/disability measure that captures both activities of daily living and instrumental activities of daily living. It consists of 20-items scored on a 0-3 scale with a summed 0-100-unit scale.

**Secondary Outcomes:** Our secondary outcomes will measure disease specific symptoms and disability:

***Patient Specific Functional Scale (PSFS):*** This measure captures items that are specific functional tasks that may be missed on standardized questionnaires. The measure consists of 5 items specifically provided by the patient. Each item provided by the patient is score from a 0 (Unable to perform task) to 10 (able to complete the activity without difficulty) scale. The PSFS is reliable, valid, and sensitive to change over time.

***Roland-Morris Disease Specific Disability Questionnaire (R-MDQ):*** We will measure the impact of patients LBP specific disability with the 24-item R-MDQ. The R-MDQ is reliable and valid and a responsive to for LBP.

***Satisfaction with Physical Function Scale:*** This is a validated 5-item questionnaire that assesses patients' satisfaction with their ability to complete basic functional tasks that are often affected by lower extremity OA, including stair-climbing, walking, doing housework (light and heavy), and lifting and carrying. All items are rated on a 7-point scale ranging from Very Dissatisfied (-3) Very Satisfied (+3).

***Physical Activity Scale for the Elderly (PASE):*** The PASE is a brief self-report, 12-item scale that measures level occupational, household and leisure activity during a one-week period. This scale has good reliability ( $r=0.68$ ) and test-re-test reliability ( $r=0.75$ ). It has also been validated for telephone administration.

***Short Physical Performance Battery (SPPB):*** The SPPB is an objective assessment of physical function. This series of functional tests has been shown to predict hospitalization, disability, nursing home placement, and declines in health and function. This test battery is relevant to the study because it assesses aspects of daily function that require lower extremity strength and are often impacted by low back pain. Specifically, this battery examines participants' balance (3 tests), gait speed (8-foot walk), and time to rise from a chair and return to the seated position five times. We will follow previously established protocols for administering and scoring each of these tests. For each test, the possible range if scores is 0-4, for a total range of 0-20 for all five tests. We will also administer the 2-minute step test. These assessments will be conducted at baseline and 12-week follow-up.

**Measures of Central Pain Sensitization:** There are a several methods for measuring central pain sensitivity. For this study we have chosen field-based tests and a self-report measure because of their potential utility for use in clinical practice:

***Pressure-Pain Threshold (PPT):*** PPT is a safe, easily administered, low cost, and validated biological marker of pain sensitivity that has been commonly used in musculoskeletal conditions. This test involves using a digital device to measure the amount of pressure experienced by a participant. Consistent with established

protocols, PPT measurements will be collected from both the left and right upper trapezius muscle and lumbar spine erector spinae musculature at the level of L5 in a systematic fashion, with the first being a practice trial. Beginning with the left side, pressure will be applied to the muscle at approximately 1Kg per second until the participants indicate self-reported pain. Trials will continue until two consecutive readings were within +/-0.4 Kg's for a maximum of four trials. The same procedure will be repeated for the right side.

***Central Sensitization Inventory (CSI):*** The CSI assesses 25 health-related symptoms common to central pain sensitization (Part A), as well as ten specific diagnoses related to central pain sensitization (Part B). It is easy to administer and was developed specifically for use in medical settings, to help identify patients with central pain sensitivity and guide treatment approaches. Part A items (which will be the focus for this study) assess the frequency of symptoms on a Likert scale of 0 (never) to 4 (always). The CSI has demonstrated strong psychometric properties (test-retest reliability=0.817, Cronbach's alpha=0.879), and CSI Part A scores differed in the expected manner among healthy patients and those with different conditions associated with central pain sensitization (fibromyalgia, chronic widespread pain, and cLBP). Recent data have also identified a clinically relevant cutoff value of 40 for CSI Part A (out of a maximum score of 100).

***Temporal pain summation and Wind-up ratio:*** Testing is conducted according to previous research and protocols. On the participant's forearm, the researcher applies a 180-gram von Frey filament once or twice to familiarize with the sensation. Then it is applied 11 times within a 1 cm diameter circle. After one touch, the participant is asked to rate the pain on a 0-100 verbal pain scale. Then ten consecutive touches are applied at random locations with a 1 second interstimulus interval and the participant is asked to rate the pain of the 10th application. The participant is also asked to provide an estimated mean over the whole series of 10 stimuli using the 0-100 verbal pain scale. The whole procedure is repeated five times. Mechanical temporal summation is calculated by subtracting the pain rating after the 1st touch from the pain rating after the 10th touch from the first round of the testing. Wind up ratio is calculated as a ratio: mean rating of the five series divided by the mean rating of the five single stimuli. These measures provide an indication if some participants perceive more pain due to enhanced nociceptive responses from repeated neural firing.

**Adherence and Feasibility Measures:** An important part of this pilot study will be collection of data regarding the interventions' feasibility and acceptability to patients. We will collect the following information:

***PA and CBT-P Logs and Telephone Call Completion:*** One important measure of feasibility will be to assess patients' adherence to the PA and PA + CBT-P programs. This will be assessed via the number of telephone calls completed, as well as performance of PA and practice of CBT-P skills. The latter will be evaluated by logs, which we will ask participants to return to the study team at the follow-up visit (or via a pre-addressed and stamped envelope if needed). We acknowledge that there are limitations to the reliability and accuracy of self-report logs. However, we believe that in this type of feasibility study it is useful to assess the degree to which participants are engaging in PA and CBT-P skills practice.

***Participant Feedback:*** We will ask participants a series of open-ended questions at the end of the program to obtain information on all aspects of the PA and CBT-P programs.

**Duke-UNC Functional Social Support Questionnaire:** The Duke-UNC Functional Social Support Questionnaire is an 8-item, self-reported, two-scale instrument assessing functional social support. Five items assess confidant support and three items assess affective support. The scales are computed by averaging the items, which are measured on a 6-point continuum.

**Revenson:** Four self-report items, used originally by Revenson and colleagues (1991), and used in further studies will assess problematic support for pain among the participant's close social relations. The items are measured on a 1-5 scale and averaged to create a composite score.

**CSQ:** The Coping Strategies Questionnaire was developed to assess coping skills in a chronic pain population. Two items assessing perceived control over pain were selected to assess this construct, consistent with the literature. The items are measured on a 1-5 scale and averaged to create a composite score.

**CES**: The Coping Efficacy Scale is a three-item, self-report scale designed to measure an individual's perceived efficacy in coping with pain. The items are measured on a 1-5 scale and averaged to create a composite score.

**ECR-R**: The Experiences in Close Relationships Scale-Revised is a self-reported measure of adult attachment, which captures both attachment avoidance and attachment anxiety. Each subscale is computed by taking the mean of 18 unique items, which are measured on a 1-5 scale.

**BFI**: The Big Five Inventory is a self-reported assessment of personality. Two subscales from the BFI were selected: neuroticism and extraversion. Subscales are computed by averaging the scores from 8 unique items, which are measured on a 1-5 scale.

**Participant Demographic and Clinical Characteristics**: These data will be collected at baseline to characterize the sample. Demographic characteristics will include self-reported age, gender, race/ethnicity, education level, income level, working status, and marital status. Clinical and health-related variables will include: BMI (calculated based on measured height and weight), duration and intensity of LBP symptoms, general self-rated health, and depressive symptoms (Patient Health Questionnaire-8). Comorbid medical conditions will be assessed using the Self-Administered Comorbidity Questionnaire. We will also administer the Coping Strategies Questionnaire and Pain Catastrophizing Scale. All clinical and health-related variables except height and weight will be self-reported.

**Analyses**: We will compare outcomes across study groups with analysis of covariance (ANCOVA) models (or non-parametric alternatives such as the Kruskal-Wallis test, when indicated), controlling for baseline values. Since this is a pilot study with small sample size, even clinically relevant differences may not be reflected as statistically significant differences (e.g. p<0.05). Therefore we will focus on effect sizes for the two intervention groups and evaluation of whether between-group difference reflects a threshold of clinical relevance. These data, along with means and standard deviations of baseline scores, correlations between baseline and follow-up scores, and attrition rate will also be used to calculate the appropriate sample size for a larger clinical trial. To address Aim 3, we will first plot baseline PPT and CSI values vs. changes in outcomes for each intervention group; we will also calculate correlations for these same associations. This will allow us to evaluate whether associations between baseline pain sensitivity measures and changes in outcomes may differ between the two intervention groups. Based on our previous experience with analyzing PPT data, we will also dichotomize these baseline scores at a <4kg vs. >=4kg to represent low and high pain sensitivity. We will then add an interaction term to our ANCOVA models (study group \* dichotomous PPT variable) to evaluate whether intervention effects vary by this indicator. If a significant interaction term is found, we will stratify the sample by this variable and explore the nature of the interaction. A similar analysis will be conducted with the established cutpoint on CSI scale or 40 out of 100.

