Another novel aspect of this project will be the evaluation of baseline pain sensitivity, measured with field-based techniques, as a potential predictor of response to the interventions. Some patients with cLBP have a lower threshold for pain, due to an augmented central pain processing mechanism. As such, measures of pain sensitivity may prove useful in understanding an ongoing refractory pain-process; it is possible that patients who have a lower threshold for pain may respond differentially to behavioral interventions. In particular, these patients may experience greater improvement when CBT-P is offered as an additional program component (compared to PA alone), since these cognitive skills have been shown to influence pain processing. This pilot study will be an important step, ultimately leading to guidance regarding whether some older adults with cLBP should be offered a PA only vs. PA + CBT-P.

To our knowledge this will be the first study to examine the home-based PA only and PA + CBT-P programs among older adults with cLBP, as well as the first to evaluate central pain sensitivity as a predictor of response to these interventions. Therefore preliminary data are needed to support a larger project. Our specific aims are:

**Specific Aim 1:** Examine the feasibility of conducting 12-week home-based, telephone-supported programs of: 1.) PA only and 2.) Combined PA+CBT-P, among older veterans (65+ years) with cLBP. Quantitative measures of feasibility will include the proportions of patients who initiate and complete the programs and adherence to in-home PA recommendations and cognitive behavioral skills practice. We will also collect in-depth qualitative information to assess aspects of the interventions that may need to be modified prior to a larger study.

**Specific Aim 2:** Collect preliminary data to evaluate the efficacy of the PA only and PA + CBT-P programs among older veterans with cLBP. Main outcomes will be an objective test of general physical function (timed up-and-go (TUG)) and self-reported physical function (PROMIS Health Assessment Questionnaire (PROMIS-HAQ)). Secondary outcomes will include: Patient Specific Functional Scale (PSFS), Satisfaction with Physical Function Scale, LBP-specific disability (Roland-Morris Low Back Pain and Disability Questionnaire (R-MDQ)), and the Coping Strategies Questionnaire.

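### Logs that point to study arm are returned by default at the visit where 12-week TUG is scored, and no step keeps the tester unaware of arm

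*Combined protocol and SAP*

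**What the plan says.** Specific Aim 2 names two primary measures: "Main outcomes will be an objective test of general physical function (timed up-and-go (TUG)) and self-reported physical function", the latter by PROMIS-HAQ. Under Measures and Data Collection, "Outcomes will be measured in person at the Durham VAMC at baseline and 12-week follow up". The SPPB and the 2-minute step test are given at the same two time points.

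Under Adherence and Feasibility Measures, telephone-call counts and logs are used to "assess patients' adherence to the PA and PA + CBT-P programs". Practice is to be judged from "logs, which we will ask participants to return to the study team at the follow-up visit", with the alternative "or via a pre-addressed and stamped envelope if needed". The CBT-P Intervention section adds, for that arm only: "Participants will be provided with a log to record their practice of these skills". No log is described for wait-list participants during the first 12 weeks.

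Under Participant Feedback: "We will ask participants a series of open-ended questions at the end of the program". Neither the person asking nor the order relative to testing is given.

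On roles, the Randomization section lets the principal investigator, the project coordinator or the physical therapist draw the envelope. It also allows the allocation to come from a table held in the tracking database. The physical therapist delivers part of the PA programme. The research assistant meets participants at baseline and is trained to measure pressure-pain threshold. No role is assigned to the 12-week TUG.

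**The concern.** TUG is a timed performance test. The start and stop of timing, the instructions and any encouragement come from whoever runs it. A tester who knows the arm can shift the result without meaning to. PROMIS-HAQ is self-reported by participants who know their arm, so masking the tester cannot protect it. TUG is the primary outcome that masking can protect.

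The Analyses section sets significance aside. It looks instead at effect sizes and at whether between-group differences reach clinical relevance, and it uses the results to size a larger trial. A shift in the 12-week TUG would therefore carry into both the judgement of promise and the next sample size.

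**Working it through.** **Does the visit expose the arm?** Setting the sections side by side:

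1. TUG, SPPB and the step test are done in person at the 12-week visit (Measures and Data Collection).
2. Log return defaults to the same visit, with mail as the fallback (Adherence and Feasibility Measures).
3. The skills log is described only for PA + CBT-P, and the logs measure adherence to the two active programmes. The set of logs brought, or their absence, therefore points to the arm.
4. Wait-list participants may choose a programme after the 12-week assessments (Study Design). If this is discussed before testing ends, it is another cue.
5. The allocation table may sit in the tracking database, which also tracks study calls and appointments. Access to electronic study data is limited to study team members, with no further limit by role (Randomization; Privacy and Confidentiality; Information Security).
6. The only use of the word blind in the text available is an eligibility exclusion for legal blindness.

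**Does baseline adjustment help?** Randomisation follows completion of all baseline assessments, so baseline TUG is scored before an arm exists. A tester bias *b* would be added to the follow-up score only. The ANCOVA contrast then estimates the true effect plus *b*.

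**How much could it matter?** The plan gives no target effect, SD, correlation or clinical threshold, so there is no figure of its own to reproduce. What follows is an illustration.

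- From the plan: 60 participants, three equal arms, hence 60/3 = 20 per arm.
- Assumed: no attrition; baseline to follow-up correlation *r* = 0.7 or 0.5; cutoff 0.3 SD; no true effect; tester bias *b* = 0, 0.1 or 0.2 SD favouring the active arm.
- Standard error of one active-versus-wait-list contrast, in SD units: SE = √[(2/20)(1 − r²)].
  - r = 0.7: √(0.1 × 0.51) = 0.226
  - r = 0.5: √(0.1 × 0.75) = 0.274
- Chance that the estimate exceeds the cutoff: 1 − Φ[(0.3 − b)/SE].

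| r | b = 0 | b = 0.1 | b = 0.2 |
|---|---|---|---|
| 0.7 | 1 − Φ(1.33) = 9% | 1 − Φ(0.89) = 19% | 1 − Φ(0.44) = 33% |
| 0.5 | 1 − Φ(1.10) = 14% | 1 − Φ(0.73) = 23% | 1 − Φ(0.37) = 36% |

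For planning, required sample size varies as 1/effect². If the true effect were 0.3 SD and the pilot estimate were inflated by 0.1 SD, the next trial would be set at (0.3/0.4)² = 56% of the size needed. These inputs are also assumed.

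**The case against.** The log instruction names the study team as recipient, not the tester, and does not say that logs change hands before testing. Several roles exist, and the research assistant, a plausible tester, is not among those who draw envelopes. A reader might infer that the plan itself unblinds the tester, or that a treating clinician does the scoring. The documents support neither. They leave both possible. What stands against the plan is the missing assignment of person, order and access.

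A reader might also infer that TUG is the trial's only protection against bias, or that tester bias would match the effects sought. Neither follows. Stratified randomisation and baseline adjustment protect against other problems, and SPPB follows established administration and scoring protocols. No target effect is stated with which to compare a bias.

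The size of tester bias cannot be derived from the documents, and the percentages largely reflect the bias put in. This is fair, and it is why they are an illustration only.

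This is a pilot whose first aim is feasibility, and participants and interventionists cannot be masked. That limits the severity. But the plan still intends to use the effect sizes, and tester bias cannot be removed once the visits have been run.

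Finally, part of the text between the significance summary and the Research Design and Methods section was not available for this check. A masking statement there cannot be ruled out.

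**Conclusion.** The point holds as an unguarded route to unblinding at the 12-week visit. It affects TUG, SPPB and the 2-minute step test, and not PROMIS-HAQ. It rests on three features of the text: the logs differ by arm, their default return coincides with outcome testing, and no tester, masking step, visit order or role-based access limit is stated. That the tester actually learns the arm is not shown.

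The size is unknown. Under the assumed inputs, a tester bias of 0.1 to 0.2 SD roughly doubles to more than triples the chance of a spurious contrast above 0.3 SD at correlation 0.7. At correlation 0.5 it raises that chance by about 1.7 to 2.6 times (23/14 and 36/14). The change is worth making because it costs little and has to be in place before the follow-up visits.

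**What to change.** - State that the 12-week TUG, SPPB and step test come first at the visit. They should be done by the research assistant, or another existing team member, who takes no part in allocation or intervention delivery and does not consult the allocation record.
- After testing, have a different team member collect logs and programme feedback. The coordinator would suit, since that role may already know the allocation.
- Keep in-person return of logs as the default and mail as the fallback. Mailing all logs could lower the return of adherence data that Aim 1 needs.
- Hold any wait-list discussion of programme choice until after testing.
- Ask participants not to mention their group to the tester. Record on the existing follow-up check sheet whether the tester became aware of it.

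Cost: wording, visit order, less flexible staffing of the visit, and possibly a small change to tracking-database permissions. No added staff, visits or participants are needed.
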